**Table 20 : Logistic regression models for subgroup analysis**

Subgroup	Subjects to be included in the model	Main effects	Result to be presented in TLFs
• Region	• All subjects from mITT Set	• Treatment, region and treatment by region interaction	P-value from the interaction between treatment and region
	• Subjects from mITT Set – Region=Western Europe	• Treatment	From comparison with placebo: • Estimated OR, • Two-sided 95% CI of the estimated OR
	• Subjects from mITT Set – Region=US	• Treatment	
	• Subjects from mITT Set – Region=ROW	• Treatment	
• MRI substudy participation	• All subjects from mITT Set	• Treatment, MRI substudy participation and treatment by MRI substudy participation interaction	P-value from the interaction between treatment and MRI substudy participation
	• Subjects from mITT Set – MRI substudy participants only	• Treatment, region	From comparison with placebo: • Estimated OR, • Two-sided 95% CI of the estimated OR
	• Subjects from mITT Set – MRI substudy non-participants only	• Treatment, region	
• Gender	• All subjects from mITT Set	• Treatment, gender and treatment by gender interaction	P-value from the interaction between treatment and gender
	• Subjects from mITT Set – females	• Treatment, region	From comparison with placebo: • Estimated OR, • Two-sided 95% CI of the estimated OR
	• Subjects from mITT Set – males	• Treatment, region	

The same missing data imputation approach will be used as the primary analysis method. An example of SAS code is available in Appendix 18.5.

In addition, a forest plot will be presented for each endpoint for the overall treatment effect and within each subgroup of interest including OR from logistic model and associated 2-sided 95% CI of OR.

Summary tables will be presented for each endpoint by subgroup, comparing each evobrutinib dose group vs placebo.

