## Evobrutinib

### Phase IIb in Rheumatoid Arthritis MS200527-0060

---

Eligible subjects will be randomized into 1 of 3 evobrutinib arms (25 mg once daily, 75 mg once daily, or 50 mg twice daily) or the placebo arm in a ratio of 1:1:1:1 stratified by whether or not they are in the MRI substudy (Yes, No) and by region (US, Western Europe, Japan, and the rest of world), so that within each treatment arm, there will be approximately 90 subjects, with approximately 45 subjects included in the MRI substudy to ensure approximately 80 evaluable subjects per arm for the primary analysis, and approximately 40 evaluable subjects per arm for the MRI analysis.

To ensure an adequate number of evaluable MRI subjects in the MRI substudy, recruitment of non-MRI subjects into the study may be capped. If a subject's baseline MRI indicates lack of osteitis and synovitis, additional subjects may be added to the MRI stratum to account for these subjects. Should the MRI substudy recruitment prove more difficult than anticipated, the Sponsor reserves the right to terminate the MRI substudy. Should this be done, all sites would be allowed to recruit non-MRI subjects into the study.

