## 7 Changes to the Planned Analyses in the Clinical Trial Protocol

- The CTP states a consistency analysis is also planned to be performed as part of the final analysis to evaluate the consistency of efficacy at Week 12 between the Japan and non-Japan subjects.

However, the decision has been taken by the Sponsor not to recruit in Japan. As a result, this consistency analysis will not be performed. Subgroup analysis on Ethnicity Japanese/Non-Japanese will not be performed either.

- In CTP version 2.0, subjects completing the Treatment Period could have entered an optional Open-Label Extension (OLE) period, but the Sponsor made the decision to not initiate the OLE (CTP version 3.0). As a result, some data have been recorded during the OLE for a subset of subjects. Safety and efficacy data from the OLE will then be summarized at the time of final analysis, as detailed in Section 12, 13, 14 and 15.
- The MRI Analysis Set has been redefined to include a pre-dose assessment.

CCI

- The CTP states that the primary endpoint will be evaluated based on a logistic regression model for the odds of ACR20 response, with evobrutinib dose group or placebo as a factor and adjustment for covariates based on randomization strata (region, MRI-substudy participation). This assumed a study design in which subjects could choose whether or not they would participate in the MRI substudy on an individual basis. However, as participation in the MRI substudy was shifted from a per-subject decision to a per-site decision (sites are either MRI or non-MRI), the selection bias is reduced and no clinically significant differences between MRI and non-MRI subjects is expected. Therefore, the adjustment for the covariate of participation in the MRI substudy has been removed. The same change in planned analysis applies for all efficacy endpoints.

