### **Primary analysis: logistic regression**

For the primary analysis, the estimate of the odds ratio (OR), together with the associated 2-sided 95% CI, nominal p-value and adjusted p-value, comparing each evobrutinib dose group to placebo, will be provided based on a logistic regression model for the odds of ACR20 response, with treatment group as a factor and adjustment based on region. An example of SAS code is available in Appendix 18.5.

Missing data will be handled using LOCF-NR as follows: each component will be imputed using post-baseline LOCF (ie, baseline value cannot be used for missing data imputation). Then the ACR20 will be re-calculated using imputed components. Subjects who prematurely discontinued from treatment will be considered as non-responders.

A family-wise Type I error rate (FWER) at the primary analysis will be controlled at the 2-sided 0.05 significance level for the 3 pairwise comparisons of evobrutinib dose versus placebo, using the Hochberg procedure (see Hochberg 1990).

The statistical test comparing each evobrutinib group to placebo can be written as follows:

$$\begin{cases} H_0: OR = 1.0 \\ H_1: OR \neq 1.0 \end{cases}$$

Consider the ordered two-sided p-values (from lowest to highest) that arise from comparing the 3 comparisons on the basis of the primary endpoint:  $p_{(1)} \leq p_{(2)} \leq p_{(3)}$ . The Hochberg's step-up method proceeds as follows:

1. Step 1: If  $p_{(3)} < 0.05$  reject  $H_{(1)}$ ,  $H_{(2)}$  and  $H_{(3)}$  (i.e., conclude all evobrutinib dose groups are more effective than placebo under the condition the OR are  $> 1$ ) and then stop; otherwise go to Step 2.
2. Step 2: If  $p_{(2)} < 0.025$  reject  $H_{(1)}$  and  $H_{(2)}$  (i.e., conclude doses associated with  $H_{(1)}$  and  $H_{(2)}$  are more effective than placebo under the condition the OR are  $> 1$ ) and then stop; otherwise go to Step 3.
3. Step 3: If  $p_{(1)} < 0.0167$  reject  $H_{(1)}$  (i.e., conclude that only one of the dose groups associated with  $H_{(1)}$  is more effective than placebo under the condition the OR is  $> 1$ ) and stop

Hochberg procedure will be computed with SAS® (see Appendix 18.5). Adjusted p-values will not be presented for any analyses based on PP analysis set.

In addition, the number and percentage of ACR20 responders (Yes/No) at Week 12 will be summarized by treatment group.

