### Logistic regression: PROC LOGISTIC with SAS

The logistic regression can be implemented using the following SAS code:

```
proc logistic data=<dataset>;  
  class TreatmentGroup(ref='Placebo') Region;  
  model AVALC(event="Y") = TreatmentGroup Region / alpha=0.05;  
  ods output ParameterEstimates=ParameterEstimates OddsRatios=OddsRatios ;  
run ;
```

A large, stylized logo consisting of the letters 'C', 'C', and 'I' in a bold, red, sans-serif font. The 'C's are slightly overlapping, and the 'I' is a simple vertical bar. The logo is centered on a solid black rectangular background.

CCI

CCI

CCI

CCI

CCI

CCI

CCI

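### SAP Table 20 leaves region out of the MRI-participation and gender interaction models, although the primary model and the odds ratios shown beside those p-values adjust for it

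*SAP*

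**What the plan says.** Protocol section 8.2 has randomisation "stratified by whether or not they are in the MRI substudy (Yes, No) and by region". SAP section 7 then drops one of these two strata from the models: "the adjustment for the covariate of participation in the MRI substudy has been removed". Region stays. The primary logistic model in SAP section 14.1 is fitted "with treatment group as a factor and adjustment based on region", and the sample code in Appendix 18.5 agrees ("TreatmentGroup Region / alpha=0.05").

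SAP section 14.3 refers to Table 20 for the subgroup models:

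- **MRI participation, interaction test on all mITT subjects:** "Treatment, MRI substudy participation and treatment by MRI substudy participation interaction".
- **Gender, interaction test on all mITT subjects:** "Treatment, gender and treatment by gender interaction".
- **Odds ratios within MRI participants, non-participants, females and males:** "Treatment, region" in all four rows.
- **Region, interaction test:** "Treatment, region and treatment by region interaction", with treatment alone in each by-region fit.

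The column heading is main effects, but the interaction is listed under it, so the column reads as the complete list of terms. Table 21 puts the odds ratios and the interaction p-value in the same display for nine endpoints, and a forest plot is planned for each endpoint.

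**The concern.** An interaction p-value printed beside a set of subgroup odds ratios is read as a test of whether those odds ratios are equal. Here it comes from a model with a different covariate set. Logistic odds ratios are non-collapsible, so leaving out a prognostic covariate changes the odds ratio even when that covariate is balanced across arms and subgroups. For MRI participation there is a second possible route. Participation is decided by site (SAP section 7; Protocol section 5.4), so the regional mix could differ between participants and non-participants.

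At stake is the coherence of the consistency display. Nine endpoints and two subgroups give 9 × 2 = 18 interaction p-values that do not test the odds ratios beside them.

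**Working it through.** **1. Terms side by side.**

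| Model | Terms |
|---|---|
| Primary (SAP 14.1, Appendix 18.5) | treatment, region |
| Within MRI yes, MRI no, female, male | treatment, region |
| MRI interaction test | treatment, MRI, treatment × MRI |
| Gender interaction test | treatment, gender, treatment × gender |
| Region interaction test | treatment, region, treatment × region |
| Within each region | treatment |

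The region block is coherent, because region is in its interaction model and constant within each by-region fit. The mismatch is confined to the MRI and gender blocks. The plan states no figure on this point to reproduce.

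**2. How far the odds ratios differ.** From SAP section 8.2.1, take 30% placebo response and a 30-point benefit. The odds ratio at fixed region is (0.60/0.40)/(0.30/0.70) = 3.50. The following are assumed, because the documents do not give them: US, Western Europe and rest-of-world shares of 15/15/70%, and region log-odds effects of -1.0/-0.7/0.

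- Placebo response by region is 0.136, 0.175 and 0.300; active response is 0.356, 0.427 and 0.600.
- Averaged over regions, placebo is 0.15×0.136 + 0.15×0.175 + 0.70×0.300 = 0.257, and active is 0.15×0.356 + 0.15×0.427 + 0.70×0.600 = 0.537.
- The odds ratio without region is (0.537/0.463)/(0.257/0.743) = 3.36, against 3.50 with region.

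A subgroup with the same regional mix on both sides, as gender may be, has 3.36 on both sides, so no spurious interaction arises. If MRI shares are 80/70/40% by region (also assumed), the regional mix is 0.238/0.208/0.554 among participants and 0.061/0.091/0.848 among non-participants. The same calculation gives 3.33 and 3.42. The ratio is 3.33/3.42 = 0.973, a log odds ratio of about -0.03 where the truth is 0.

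**3. Effect on the test.** Simulation: 360 subjects, four equal arms, 3-df likelihood-ratio test, 1,000 trials in each of 12 scenarios. Region shares were 15/15/70%, region effects ranged from none to -1.0/-0.7/0, and MRI share was either 50% everywhere or 80/70/40%. The assumed interaction was 0 or -1.0 on the log-odds scale.

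| Quantity | Without region | With region |
|---|---|---|
| Rejection at 0.05, no interaction | 0.036 to 0.055 | 0.036 to 0.054 |
| Power, log-odds interaction -1.0 | 0.267 to 0.347 | 0.283 to 0.346 |

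Within a single scenario, adding region changed power by between 0.283 - 0.292 = -0.009 and 0.298 - 0.267 = +0.031. The p-value moved by a median of 0.006 to 0.047, with a 95th percentile of 0.05 to 0.20. The call at 0.05 differed in 0.5% to 6% of trials.

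**4. Does a region main effect bring the test closer to the display?** The joint model equivalent to the separate within-subgroup fits contains region and region × subgroup. The scenario here is a more extreme one with no interaction: region shares 10/15/75%, placebo response 20/25/50%, MRI share 80/80/40%. The median distance of the p-value from that matching model was 0.069 without region and 0.022 with region as a main effect. The gap narrows but does not close.

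**The case against.** The strongest reply is that nothing depends on this. Protocol section 8.5.4.7 calls the subgroup analyses descriptive, SAP section 14.3 uses them to look at consistency, and no rule acts on the interaction p-value. That stands, and it limits the point to an optional improvement.

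A reader might infer that the omission materially biases the interaction test or costs it power. The documents do not support that. They give no region effects and no MRI share by region. Protocol section 5.4 states that MRI and non-MRI sites do not differ systematically beyond MRI availability, and nothing ties gender to region. Randomisation is stratified by both MRI participation and region, so omitting region does not confound treatment within either MRI subgroup. The shift in step 2 is about -0.03, against a sampling SD of about 0.5 for the averaged interaction estimate. Power comparisons are not stable in sign. Under the 20/25/50% placebo picture and a true interaction ratio of 0.35, one run of 800 trials went from 36.8% to 39.3% with region, and another of 1,500 trials (active log odds ratio 1.25) went from 38.5% to 37.7%. With placebo rates of 30/35/45%, inside the planned 30% to 45%, power was 39.1% both ways.

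Two further replies stand in part. Table 20 points to subgroup code in Appendix 18.5, most of which is redacted, so the implemented model cannot be checked. If that code contains region, the table needs correcting instead. Table 21 also pairs region-adjusted odds ratios with a non-stratified Miettinen-Nurminen interval, so the display is already mixed. That does not explain leaving region out of the test that accompanies the odds ratios.

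**Conclusion.** The inconsistency is plain on the face of Table 20 and is unexplained: two of the three interaction tests omit a stratum that the primary model and the accompanying odds ratios include. These p-values test equality of odds ratios not adjusted for region, which differ from the displayed ones whenever region is prognostic (3.36 against 3.50 in the illustration). The consequence is small: type I error stays near 5%, and any power gain is negligible to slight. No material bias or loss of power is claimed. The sizes rest on assumed region shares, region effects and MRI shares; the mismatch of terms rests on no assumption. What remains is that an individual p-value can look at odds with its own forest plot for no reason other than the model terms.

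**What to change.** In SAP Table 20, add region as a main effect to the MRI-participation and gender interaction models for all Table 21 endpoints, in line with the primary model, and make any subgroup code in Appendix 18.5 agree. If region is left out on purpose, state why. If the p-value is meant to test exactly the odds ratios from the separate within-subgroup fits, region × subgroup is needed as well.

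The cost is one covariate in two model statements. No new data are needed and the primary analysis is untouched. Sparse endpoints are no obstacle to the main effect, because the smaller within-subgroup models already carry region.

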**Table 21 : Subgroup Analysis – Endpoints**

Endpoints	Analysis	Analysis method	Description	Missing data handling

 
• ACR 20/50/70
 
• DAS28-hsCRP < 2.6
 
• DAS28-hsCRP < 3.2
 
• EULAR Boolean Remission
 
• CDAI ≤ 2.8
 
• SDAI ≤ 3.3
 
• EULAR Responder Index [good/moderate, vs no response]
 
	
 
• Week 12
 
	Logistic regression	Presentation of response rate for each treatment group, Δ in response rate compared to placebo, 2-sided 95% CI of Δ (non-stratified MN), OR, 2-sided 95% CI of OR, p-value of interaction between treatment and subgroup of interest	LOCF-NR*

\* LOCF-NR: post-baseline last observation carried forward. At Week 12, patients who discontinued from treatment are considered as non-responders.

## 14.4 Open-label Extension

Efficacy Data from OLE will be listed on subjects from mITT set who entered in the OLE.

## 15 Safety Evaluation

The subsections in this section include specifications for summarizing safety endpoints that are common across clinical trials such as AEs, laboratory tests and vital signs. As detailed in Section 7, some subjects have entered in the OLE, even if the Sponsor decided not to initiate the OLE in protocol V3.0. As a result, for all safety endpoints, data selection will be handled as indicated in Table 22.

**Table 22 : Data Handling for Safety Analysis**

Population	Period covered	Treatment groups	Data to be analyzed
SAF	12-week treatment period	
 
Placebo
 
Evobrutinib 25 mg QD
 
Evobrutinib 75 mg QD
 
Evobrutinib 50 mg BID
 
	All Data collected during the 12-week treatment period, safety follow-up included
Subjects with at least 1 dose during OLE	OLE period only	
 
Placebo/Evobrutinib 50 mg BID
 
Evobrutinib 25 mg QD/Evobrutinib 50 mg BID
 
Evobrutinib 75 mg QD/Evobrutinib 50 mg BID
 
Evobrutinib 50 mg BID/Evobrutinib 50 mg BID
 
	Data from OLE period only including all Safety follow-up data posterior to OLE (Safety follow-up / End of Study)

### 15.1 Adverse Events

All analyses described in this section will be based on treatment-emergent adverse events (TEAEs) if not otherwise specified. TEAEs will be defined according to Table 23. AEs from the OLE period will be listed only (those with a start date after the first intake during the OLE).

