### 6.2 Final Analysis

The final analysis will be triggered when 100% of subjects randomized either complete the Week 12 visit or discontinue prematurely prior to Week 12, the protocol violations are determined, and the database is locked. All data collected from the Safety follow-up visit during the double-blind 12-week treatment period will be included.

Data collected during the OLE period from earlier versions of the protocol will not be part of the Final analysis for the 12 Weeks treatment period but be summarized separately (See Section 7).

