### Treatment day:

Treatment day is defined as relative day to the start date of treatment. Treatment day will be calculated accordingly, ie:

- For the 12 weeks treatment period, treatment day 1 is defined as the date of first administration of any IMP.
- For the OLE period, treatment day 1 is defined as the date of first administration of evobrutinib 50 mg BID during OLE.

The day before is defined as Treatment day –1 (no Treatment day 0 is defined).

Treatment day will only be presented in subject safety data listings. In these listings, the difference (in days) between an event (eg, AE or laboratory assessment) and the first administration will be calculated as follows:

- If the event is posterior to the first IMP administration, the difference is equal to Date of event – Date of first IMP administration + 1
- Otherwise, the difference is equal to Date of first IMP administration – Date of event

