### 10.1 Disposition of Subjects and Discontinuations

A table on screened subjects describing the number and percent of subjects in each disposition category will be produced by treatment group. These categories are summarized below:

- Total number of screened subjects, ie subjects that gave informed consent (overall summary only)
- Number of subjects who discontinued prior to randomization and reason (overall summary only)
- Number of randomized subjects
- Number of randomized subjects who did not start treatment
- Number of randomized subjects who permanently discontinued treatment during 12-week treatment period and reason (as reported in the eCRF)
  - Number of randomized subjects who completed safety follow-up period
  - Number of randomized subjects who discontinued from trial during safety follow-up and reason
- Number of randomized subjects who completed 12-week treatment period
  - Number of randomized subjects who completed safety follow-up period
  - Number of randomized subjects who discontinued from trial during safety follow-up and reason
- Number of randomized subjects who signed OLE informed consent under previous versions of the protocol

A table based on screened subjects, describing the number and percent of subjects set by treatment group, will be produced, with the following categories:

- Number of screened subjects
- Number of subjects included in the ITT Analysis Set
- Number of subjects included in the SAF
- Number of subjects included in the mITT Analysis Set
- Number of subjects in MRI Analysis Set
- Number of subjects included in the PP Analysis Set
- Number of subjects included in the MRI PP Analysis Set

- Number of subjects included in the QoL Analysis Set

CCI

- Number of subjects who received at least 1 dose in the OLE under previous versions of the protocol

A table based on screened subjects, describing the number and percent of subjects in each region (Western Europe, US, ROW), country within region, site within country, by analysis set, will be produced.

Another table based on randomized subjects will provide the number and percent of subjects by randomization strata and country. The different randomization strata are listed below:

- MRI substudy participation
  - Yes
  - No
- Region
  - US
  - Western Europe
  - Rest of the world

Corresponding individual listings will be prepared:

- Discontinued subjects (from treatment or study) will be listed with their reason for withdrawal (from treatment or study).

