## 12 Previous or Concomitant Medications/Procedures

Previous or concomitant medications during the 12 weeks treatment period will be summarized using the SAF.

As detailed in Section 7, some subjects have entered in the OLE, even if the Sponsor decided not to initiate the OLE in protocol V3.0. Therefore, concomitant medications during OLE will also be summarized for subjects who received at least 1 dose in the OLE under previous versions of the protocol.

The definition of previous or concomitant medications is presented in [Table 9](#):

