**Table 9: Definition of Previous/Concomitant Medications**

Analysis Set	Period covered	Treatment groups	Definition
SAF	12-week treatment period	
 
• Placebo
 
• Evobrutinib 25 mg QD
 
• Evobrutinib 75 mg QD
 
• Evobrutinib 50 mg BID
 
	
Previous medications are medications, other than trial medications, which either:
 
 
1. started and stopped before first administration of any IMP (placebo or evobrutinib) or
 
2. started prior to the first administration of IMP (placebo or evobrutinib) and are taken by subjects on or after the first administration of IMP.
 

			
Concomitant medications are medications, other than IMPs, which either:
 
 
1. started on or after the first administration of any IMP (placebo or evobrutinib) or
 
2. started prior to the first administration of IMP (placebo or evobrutinib) and are taken by subjects on or after the first administration of IMP.
 

Subjects with at least 1 dose during OLE	OLE	
 
• Placebo/Evobrutinib 50 mg BID
 
• Evobrutinib 25 mg QD/Evobrutinib 50 mg BID
 
• Evobrutinib 75 mg QD/Evobrutinib 50 mg BID
 
• Evobrutinib 50 mg BID/Evobrutinib 50 mg BID
 
	
Concomitant medications are medications, other than IMPs, which either:
 
 
1. started on or after the first administration of evobrutinib during OLE or
 
2. started prior the first administration of evobrutinib during OLE and are taken by subjects on or after the first administration of evobrutinib during OLE.
 

Partial dates will be handled as follows:

- For previous medications, in case the date values will not allow a medication to be unequivocally allocated to previous medication, the medication will be considered as previous medication.
- For concomitant medications, in case the date values will not allow a medication to be unequivocally allocated to concomitant medication, the medication will be considered as concomitant medication.

The ATC-2nd level and PT will be tabulated as given from the World Health Organization Drug Dictionary (WHO-DD) current version. In case multiple ATCs are assigned to a drug, all ATC2nd level will be used for reporting.

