**Table 23: Definition of TEAE**

Treatment group	Period covered	Definition

 
Placebo
 
Evobrutinib 25 mg QD
 
Evobrutinib 75 mg QD
 
Evobrutinib 50 mg BID
 
	12-week treatment period	
TEAEs will be defined as:
 
 
AEs starting on or after first treatment administration of any IMP (placebo or evobrutinib) during the 12-week treatment period (safety follow-up included)
 
or if it was present prior to any IMP administration but exacerbated after.
 
 
Any AE which started before study first treatment administration of any IMP (placebo or evobrutinib), but improved during treatment period, will not be counted as TEAE.

For the purpose of defining the TEAE flag, incomplete AE-related dates will be handled as follows:

- In case the onset date is missing completely or missing partially but the onset month and year, or the onset year are equal to the start of IMP then the onset date will be replaced by the minimum of start of IMP and AE resolution date.
- In all other cases the missing onset day or missing onset month will be replaced by 1.
- Incomplete stop dates will be replaced by the last day of the month (if day is missing only), if not resulting in a date later than the date of subject's death. In the latter case, the date of death will be used to impute the incomplete stop date.
- Further information collected after the cut-off for an analysis (such as a fatal outcome) may be extracted from the Safety data base and presented separately in the CSR.

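### The OLE adverse-event rule, read as dates, leaves out the first open-label dose day, and OLE adverse events get no descriptive count

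*SAP*

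**What the plan says.** SAP 15.1 bases the adverse-event analyses on TEAEs unless otherwise specified and then sets a rule for the extension: "AEs from the OLE period will be listed only (those with a start date after the first intake during the OLE".

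Table 23 defines a TEAE for the 12-week period only. Its first limb is "AEs starting on or after first treatment administration of any IMP (placebo or evobrutinib) during the 12-week treatment period (safety follow-up included". It has no OLE row.

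Three other places set the context for the boundary and the reporting:

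- **OLE day 1** (SAP 9.6): "For the OLE period, treatment day 1 is defined as the date of first administration of evobrutinib 50 mg BID during OLE".
- **OLE concomitant medications** (SAP Table 9): a medication counts if it "started on or after the first administration of evobrutinib during OLE or" was started earlier and is still being taken then.
- **General statements on OLE data:** SAP 6.2 says the data "will not be part of the Final analysis for the 12 Weeks treatment period but be summarized separately" and refers to Section 7. Section 7 says "Safety and efficacy data from the OLE will then be summarized at the time of final analysis" and refers on to Sections 12 to 15 for detail.

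The detail sections do tabulate several OLE items. Section 10.1 gives the "Number of subjects who received at least 1 dose in the OLE under previous versions of the protocol". Section 12 states that "concomitant medications during OLE will also be summarized for subjects who received at least 1 dose in the OLE". Section 13.1 summarizes OLE exposure, and Section 15.3 summarizes laboratory findings separately for the OLE. Table 22 selects OLE data by sequence group for all safety endpoints.

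**The concern.** Two things look wrong.

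The first is the boundary. The OLE listing takes events that start *after* the first OLE intake, while the neighbouring rules take events or medications that start *on or after* the relevant first dose. Table 23 gives no date at which the 12-week window ends for someone who goes on to open-label drug. An event starting on the first open-label day can therefore miss the OLE listing and be tabulated under the 12-week arm. For a former placebo subject, an event on the first day of active drug could then be counted as a placebo event.

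The second is the missing count. The report would show how many subjects were dosed in the OLE, for how long, with which medications and with what laboratory results. It would not show how many had any adverse event, a serious one, or one leading to withdrawal.

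**Working it through.** The plan gives no figure to reproduce here. The check compares the rules and tests them at the boundary.

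**Boundary.** Let F be the date of the first OLE dose and S the start date of an adverse event. By SAP 9.6, OLE treatment day = S − F + 1 for events from F onward.

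| Rule | Condition on dates | First OLE day captured | Event with S = F |
|---|---|---|---|
| OLE AE listing (15.1), read as dates | S > F | day 2 | left out |
| OLE medications (Table 9), start-date limb | S ≥ F | day 1 | kept |
| *On or after* wording of Table 23, if applied to the OLE | S ≥ F | day 1 | kept |

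The difference is 2 − 1 = 1 calendar day per OLE subject.

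**Where a day-1 event goes.** Its start date is later than the first 12-week dose, so it meets the lower limit in Table 23. The upper limit is described only as the 12-week treatment period with safety follow-up, not as a date before F. Nothing explicit keeps the event out of the 12-week tables, and the 15.1 rule, read as dates, does not claim it for the OLE.

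**What happens on that day.** OLE subjects take 50 mg twice daily, which is 2 × 50 = 100 mg/day. SAP Table 4 gives four sequence groups:

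- placebo: 0 to 100 mg/day
- 25 mg QD: 25 to 100 mg/day
- 75 mg QD: 75 to 100 mg/day
- 50 mg BID: 100 to 100 mg/day

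The daily dose rises in 3 of the 4 groups, and for former placebo subjects it is the first active dose in the trial.

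**Planned counts.** Table 25 has 14 rows: two overviews, all TEAEs, IMP-related TEAEs, AESIs, IMP-related AESIs, serious, IMP-related serious, non-serious, leading to death, IMP-related leading to death, leading to withdrawal of IMP, leading to study termination, and exposure-adjusted rates (2 + 12 = 14). These rest on TEAEs, which Table 23 confines to the 12-week period, and the serious-event tabulation in 15.2.2 is also of TEAEs. The number of adverse-event tables planned for the OLE is 0. The 14 describes the layout of the plan and does not measure impact.

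**Number affected.** SAP 7 says only that a subset of subjects has OLE data. Without the subset's size or an event rate, the number of day-1 events cannot be estimated.

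**The case against.** A reader might infer that Sections 6.2 and 7 contradict 15.1. The documents do not support that. Section 6.2 points to Section 7, Section 7 points to Sections 12 to 15, and 15.1 then states the rule that operates. The general statement is also largely kept, since OLE exposure, medications and laboratory data are summarized. Listing is a consistent choice for a cancelled, uncontrolled extension: OLE efficacy (14.4) and OLE protocol deviations (10.2) are listed, and OLE compliance is not analysed (13.2). This stands. What remains is a gap in coverage: adverse events are left without a count while related OLE safety data have summaries.

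The stronger challenge is to the boundary. An intake is a moment, so an event a few hours after the tablet is after it. The treatment-day formula in 9.6 also points that way. It adds 1 for events posterior to the first administration and otherwise takes the plain date difference. A same-day event treated as otherwise would be day 0, which the SAP says does not exist. So *posterior* in that formula must include the same date, and *after* in 15.1 might be read alike. That makes the date reading arguable but does not settle it. Section 15.1 refers to a start date, and the SAP writes *on or after* elsewhere when it means to include the day. Protocol 7.4.1.2 asks for onset times only when important, and 15.1 does not say to use them.

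It is also fair that *on or after* alone would move into the OLE events that began earlier the same day, before the first open-label tablet. The fix has to deal with this.

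**Conclusion.** The boundary point holds as a minor defect in a stated rule, and the missing count as a minor gap. Read as dates, the rule omits one calendar day per OLE subject, the day of first open-label dosing, and lets an event starting then be counted under the former arm. This rests on comparing calendar dates and on Table 23 not ending at the first OLE dose. If the programmers use recorded onset times, or read *after* to include the same day, the listing gap closes, but the SAP does not tell them to do either.

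A reader might go further and infer that open-label events disappear or that the trial's conclusions are at risk. The documents do not support either. SAP 9.2 puts all recorded data in individual listings, so no event leaves the report. SAP 15.2.1 counts all deaths without limiting the period. The randomized efficacy comparison is unaffected. The possible harm is limited to first-dose-day events being placed in the wrong period, plus the absence of a simple count. The size of the OLE subset is not given, so neither can be quantified.

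**What to change.** 1. **Add an OLE row to Table 23:** adverse events starting on or after the first OLE dose, through the post-OLE safety follow-up. Where a recorded time shows onset before the first OLE tablet that day, leave the event in the 12-week period. Pre-existing events that worsen on open-label drug could be added only where the date of worsening was recorded, which the documents do not show.
2. **Use that row twice:** to select the OLE listing in 15.1, and to end the 12-week TEAE window for subjects who entered the OLE, so that each event falls in one period.
3. **Add one descriptive overview** by OLE sequence group and total, with five rows: any AE, serious, Grade 3 or higher, leading to withdrawal of IMP, leading to death. The denominator is the number dosed in the OLE, already tabulated under SAP 10.1. The size is 5 rows × (4 groups + total) = 25 counts.

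If the sponsor prefers a listing only, the first two changes are still needed, and Sections 6.2 and 7 should say that OLE adverse events are listed.

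The cost is one table row and one small table from data already collected. The downside is an uncontrolled table with possibly very small cells, from which no inference should be drawn.
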